Observational and Non-Interventional Study (ONIS) using Existing Data Protocol

Document Number:	
BI Study Number:	1199-0541
BI Investigational Product(s):	N/A
Title:	Assessment of the Oxygen Use and Future Outcomes Associated with Oxygen Use in Patient with Fibrotic Interstitial Lung Disease
Brief lay title:	Oxygen Therapy Use in Patients with Fibrotic ILD
Protocol version identifier:	6.0
Date of previous version of protocol:	29 JUN 2023
PASS:	N/A
EU PAS register number:	N/A
Active substance:	N/A
Medicinal product:	N/A
Product reference:	N/A
Procedure number:	N/A
Marketing authorisation holder(s):	 C: 

	P: [REDACTED]
Joint PASS:	N/A
Research question and objectives:	
The purpose of this study is to examine oxygen therapy utilization and assess the impact of oxygen therapy on clinical and economic outcomes of ILD patients. There are three aims for this project:
 
Aim 1: To describe initiation and use of oxygen therapy among patients with fibrotic ILD. The specific objectives for Aim 1 are to:
 
 • Examine the incidence and prevalence of oxygen therapy among patients with fibrotic ILD • Assess the time to first oxygen therapy among fibrotic ILD patients naive to oxygen therapy, and examine factors/variables associated with oxygen therapy initiation 
Aim 2: To assess the impact of oxygen therapy on clinical outcomes among patients with fibrotic ILD. The specific objective for Aim 2 is to:
 
 • Evaluate the impact of oxygen therapy initiation on clinical outcomes, including disease progression and mortality, among fibrotic ILD patients 
Further Aim: To assess the impact of oxygen therapy on economic outcomes among patients with fibrotic ILD. The specific objective for this aim is to:
 
 • Evaluate the impact of oxygen therapy initiation on health care resource utilization (HCRU) and healthcare costs among fibrotic ILD patients
Country(-ies) of study:	United States
Author:	[REDACTED]
Marketing authorisation holder(s):	
In case of PASS, add: MAH contact person:	N/A
In case of PASS, add: <EU-QPPV:>	N/A
In case of PASS, add: <Signature of EU-QPPV:>	N/A

Date:	July 7 th , 2023
--------------	-----------------------------

Page 1 of 40**Proprietary confidential information****© 2024 Boehringer Ingelheim Group of companies. All rights reserved.**

1. LIST OF ABBREVIATIONS

AHRQ	Agency for Healthcare Research and Quality
CI	Confidence Interval
COPD	Chronic Obstructive Pulmonary Disease
CPI	Consumer Price Index
CPT	Current Procedural Terminology
CT	Computed Tomography
DLCO	Diffusing Capacity for Carbon Monoxide
EHR	Electronic Health Record
ER	Emergency Department
ENCePP	European Network of Centres for Pharmacoepidemiology and Pharmacovigilance
FEV ₁	Forced Expiratory Volume in 1 Second
FVC	Forced Vital Capacity
GLM	Generalized Linear Models
HCPCS	Healthcare Common Procedure Coding System
HCRU	Health Care Resource Utilization
HIPAA	Health Information Portability and Accountability Act of 1996
HP	Hypersensitivity Pneumonitis
ICD-9-CM	International Classification of Diseases, Ninth Revision, Clinical Modification
ICD-10-CM	International Classification of Diseases, Tenth Revision, Clinical Modification
IIP	Idiopathic Interstitial Pneumonia
ILD	Interstitial Lung Disease
IPF	Idiopathic Pulmonary Fibrosis
IPTW	Inverse Probability of Treatment Weighting
KM	Kaplan-Meier
LTOT	Long-Term Oxygen Therapy
MAH	Marketing Authorization Holder
NIS	Non-Interventional Study
PASS	Post-Authorization Safety Study
PFT	Pulmonary Function Test
PS	Propensity Score
PSM	Propensity Score Matching
SD	Standard Deviation
SpO ₂	Oxygen Saturation

2. RESPONSIBLE PARTIES

2.1.1 ABSTRACT

Name of company: Boehringer Ingelheim			
Name of finished medicinal product: NA			
Name of active ingredient: NA			
Protocol date: 07 JUL 2023	Study number:	Version/Revision:	Version/Revision date:
Title of study: Oxygen Therapy Use in Patients with Fibrotic ILD			

Rationale and background:
 
Interstitial lung disease (ILD) is a broad term that describes more than 200 diverse lung disorders, including idiopathic pulmonary fibrosis (IPF), autoimmune ILD, Nonspecific Interstitial Pneumonia (NSIP), hypersensitivity pneumonitis (HP), and sarcoidosis. Typical symptoms of ILD include cough and dyspnea, as well as decreased lung capacity, which leads to exercise intolerance and hypoxemia.
 
The major goal of therapy in ILD patients is to slow disease progression as well as to improve the associated dyspnea, exercise capacity, and health-related quality of life. Approved treatment options for fibrosing ILD comprise antifibrotic treatments including nintedanib and pirfenidone, which slow the rate of decline in forced vital capacity (FVC). Other commonly prescribed treatment options are corticosteroids, immunosuppressants, opioids, and lung transplantation. Despite advances in pharmacotherapy, many patients continue to have disease progression.
 
Supplemental oxygen (O₂) is commonly prescribed in clinical practice for patients with fibrotic ILD to reduce breathlessness and increase physical capacity; however, robust evidence to support its long-term use is lacking. Recommendations for long-term oxygen therapy (LTOT) for resting hypoxemia in ILD are largely extrapolated from trials conducted in chronic obstructive pulmonary disease (COPD), where a survival benefit is well established. The American Association for Respiratory Care guideline recommends the use of oxygen therapy to maintain the oxygen saturation (SpO₂) range of 94–98% for most hospitalized patients. Despite its frequent use, there is a paucity of studies evaluating the incidence, prevalence, and impact of LTOT on outcomes such as disease progression or mortality in ILD. This study will help fill in the gaps in increasing the understanding of the use of oxygen therapy among fibrosing ILD patients and assess whether the use of oxygen leads to better or worse outcomes.
			

Research question and objectives:

The purpose of this study is to examine oxygen therapy utilization and assess its impact on clinical and economic outcomes of ILD patients. There are three aims for this project:

Aim 1: To describe initiation and use of oxygen therapy among patients with fibrotic ILD. The specific objectives for Aim 1 are to:

- Examine the incidence and prevalence of oxygen therapy among patients with fibrotic ILD
- Assess the time to first oxygen therapy among fibrotic ILD patients naive to oxygen therapy, and examine factors/variables associated with oxygen therapy initiation

Aim 2: To assess the impact of oxygen therapy on clinical outcomes among patients with fibrotic ILD. The specific objective for Aim 2 is to:

- Evaluate the impact of oxygen therapy initiation on clinical outcomes, including disease progression and mortality, among fibrotic ILD patients

Study design:

This is a non-interventional study of patients enrolled in a commercial, Medicaid, or Medicare plan, using existing administrative claims and electronic health record (EHR) data in Optum's Market Clarity Integrated Claims + Clinical database for the period of 01 October 2015 through 30 June 2022 (study period). The study period may be extended though latest data available at the time of study implementation to increase study sample.

Patients aged ≥ 18 years with newly diagnosed fibrosing ILD will be identified from 01 October 2016 through 30 June 2022 (patient identification period). Patients will be required to have 12 months of baseline continuous enrollment prior to fibrosing ILD diagnosis for collecting patient demographics and clinical characteristics. The pre-ILD baseline period will also be used to describe baseline prevalence of oxygen therapy use. To describe the initiation and use of oxygen therapy after first fibrosing ILD diagnosis (Aim 1), patients will be followed for a variable period from the fibrosing ILD diagnosis date until the earlier of disenrollment from the health plan, end of study period, or death. Oxygen therapy use will be described, and results will be stratified by underlying cause of fibrosis (e.g., IPF vs. non-IPF ILD). Factors associated with initiation of oxygen therapy will be assessed using multivariable methods.

To assess the impact of oxygen therapy use on outcomes (Aim 2 [REDACTED]), patients with fibrosing ILD who initiated oxygen therapy will be propensity score matched to those who did not yet initiate oxygen therapy. The index date will be defined as the date of oxygen therapy initiation for oxygen therapy cohort, or a date that is eligible for index and is similar to the matched case's index date for no oxygen therapy cohort. Disease progression, acute exacerbations, [REDACTED]

Population:	
This study will include patients newly diagnosed with fibrosing ILD between 01 October 2016 through 30 June 2022.
 
Study Population: Aim 1
 
The analysis for Aim 1 will include patients newly diagnosed with fibrosing ILD during the patient identification period. Patients must meet the following selection criteria to be included in the study:
 
Inclusion Criteria
 
• ≥ 2 fibrosing ILD diagnoses in any position on different dates of service, within 365 days of each other, and in the same continuous enrollment period during the patient identification period. The fibrosing ILD diagnosis date will be defined as the date of the first fibrosing ILD diagnosis. The two fibrosing ILD diagnosis codes can be one of the following combinations:
○ 2 fibrosis codes○ 1 fibrosis code & 1 ILD code that requires fibrosis code• ≥ 18 years of age as of the fibrosing ILD diagnosis date• Continuous enrollment with medical and pharmacy coverage for 12 months prior to the fibrosing ILD diagnosis date (pre-ILD baseline period) 
Exclusion Criteria
 
• Fibrosing ILD diagnosis in the 12-month pre-ILD baseline period• Unknown gender, geographic region, or insurance type 
Cohort Assignment
 
Patients meeting initial selection criteria for Aim 1 will be assigned to cohorts based on known cause of fibrosis:
 
• IPF—≥ 2 medical claims with diagnosis for IPF in any position during the study period• Non-IPF ILD—< 2 medical claims with diagnosis for IPF during the study period 
Study Population: Aim 2
 
The analysis for Aim 2 and Further Aim will include patients identified for Aim 1 who meet the following additional selection criteria. Final oxygen therapy cohorts will be determined during the propensity score matching (PSM) procedure.
 
• Oxygen therapy cohort
○ ILD patients with ≥ 1 medical claim for oxygen therapy after fibrosing ILD diagnosis. The index date will be defined as the first date of a claim for oxygen therapy.• No oxygen therapy cohort
○ Matched to a patient in the oxygen therapy cohort. The index date will be assigned as a date that is eligible to set an index
--------------------	---

date (i.e., similar to the matched oxygen therapy patient in time from the fibrosing ILD diagnosis date to the index date, and during the same continuous enrollment period as the fibrosing ILD diagnosis date).

NOTE: Following review of results from Aim 1, the study team will determine whether continuous enrollment criteria for Aim 2 and Further Aim requires revision.

Variables:	
Aim 1
 
Outcomes: time to initiation of oxygen therapy; time to sustained oxygen therapy use; sustained oxygen therapy use within the first 12 months of follow-up
 
Baseline covariates: demographic characteristics (age, sex, race/ethnicity, geographic region, insurance type, index year), clinical characteristics (underlying ILD type; respiratory diseases; other clinical characteristics; Quan-Charlson comorbidity score; Agency for Health Research and Quality [AHRQ] comorbid conditions; smoking; pulmonary rehabilitation) healthcare utilization characteristics (provider specialty; medication use; all-cause HCRU; all-cause health care costs)
 
Stratification: IPF vs non-IPF ILD
 
Aim 2 [REDACTED]
 
Exposure: oxygen therapy vs no oxygen therapy
 
Primary Outcomes: Time to disease progression; time to all-cause mortality; time to hypoxemia, time to acute exacerbations, counts of acute exacerbations
 
[REDACTED]
 
Baseline covariates: demographic characteristics (index year, age, sex, race/ethnicity, geographic region, insurance type), clinical characteristics (underlying ILD type; respiratory diseases; other clinical characteristics; Quan-Charlson comorbidity score; AHRQ comorbid conditions; smoking; pulmonary rehabilitation) healthcare utilization characteristics (provider specialty; medication use; all-cause HCRU; all-cause health care costs)

Data sources:	
Optum's Market Clarity Integrated Claims + Clinical database Research Database, a fully de-identified and HIPAA compliant database in which clinical data are combined with adjudicated medical and pharmacy claims from both Optum-affiliated and non-affiliated payers. The Market Clarity dataset links EHR data with historical, linked administrative claims data, pharmacy claims, physician claims, facility claims (with clinical information), medications prescribed and administered, diagnoses, procedures, and information derived from clinical notes using NLP. For this study, the subset of individuals with health plan enrollment data available will be used. Insurance coverage will include commercial, Medicaid, and Medicare.

Study size:	
Using data from Optum's Market Clarity Integrated Claims + Clinical database from 01 Jan 2016 - 31 May 2022, 1,179,017 patients with fibrosing-ILD were identified. Among them, 34,299 adult patients had at least one claim for oxygen therapy with 6 months of continuous enrollment in claims and 6 months of continuous activity in EHR. These counts are for informational purposes only and may not reflect the final sample size. Application of other inclusion and exclusion criteria required for this study or other factors may reduce the sample size.

Data analysis:	
Aim 1 Analysis
 
Descriptive Analysis
 
All variables will be analyzed descriptively, and results will be stratified by cohort (IPF vs non-IPF ILD). Numbers and percentages will be provided for categorical variables. Means, medians, and standard deviations, will be provided for continuous variables. Appropriate statistical comparisons will be conducted based on the distribution of the measure.
 
Kaplan-Meier Analysis
 
Kaplan-Meier (KM) analysis will be used to evaluate time to oxygen therapy initiation from the fibrosing ILD diagnosis date among patients without baseline oxygen therapy use. When KM analysis is conducted, results will include censored-adjusted percentage of patients who have the event of interest at pre-specified time periods of interest (e.g., 6 month, 9 months, 12 months). In addition, the median (and 25th and 75th percentile) time to event and the 95% confidence interval (CI) around the median (and 25th and 75th percentile) will be reported. Censoring will occur at the first of the following: disenrollment from the health plan, end of the study period, or death.
 
Graphs of the cumulative incidence functions (i.e., $1-S(t)$ where $S(t)$ is the survival function) will be presented along with the cumulative percentage of patients with oxygen therapy initiation following the fibrosing ILD diagnosis date. Methods may account for competing events (e.g., death as competing event for oxygen therapy initiation).
 
Multivariable Analysis
 
Cox proportional hazards regression will be used to identify factors associated with initiation of oxygen therapy. Covariates included in the adjusted model will be determined based on statistical significance and clinical rationale. Baseline covariates may include:
 
• Demographic characteristics: index year, age group, gender, race/ethnicity, insurance type, geographic region• Baseline clinical characteristics: all-cause HCRU, all-cause health care costs, medication use, respiratory disease, Quan-Charlson comorbidity score, AHRQ comorbid conditions, smoking, provider specialty, pulmonary rehabilitation 
Following standard procedures, regression diagnostics will be performed for each model to assess goodness of fit and violations of model assumptions (e.g. multicollinearity, non-proportionality). Violations of the model assumptions will be documented, and appropriate corrections will be made to the analysis. Hazard ratios and associated 95% CIs and p-values will be reported for all covariates in the model.
 
[REDACTED]
 
[REDACTED]
 
[REDACTED]

-----------------------	--

Milestones:	Start of data extract: AUG 2023
	End of data analysis: DEC 2023
	Final report of study results: FEB 2024

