7.2 SETTING

7.2.1 Secondary data source selection

The study will use administrative claims and EHR data from Optum's Market Clarity Integrated Claims + Clinical database.

7.2.2 Study population: Aim 1

The analysis for Aim 1 will include patients newly diagnosed with fibrosing ILD during the patient identification period. Patients must meet the following selection criteria to be included in the study:

Inclusion Criteria

- ≥ 2 fibrosing ILD diagnoses in any position on different dates of service, within 365 days of each other, and in the same continuous enrollment period during the patient identification period. The ***fibrosing ILD diagnosis date*** will be defined as the date of the first fibrosing ILD diagnosis. The two fibrosing ILD diagnosis codes can be one of the following combinations:
 - 2 fibrosis codes
 - 1 fibrosis code & 1 ILD code that requires fibrosis code
- ≥ 18 years of age as of the fibrosing ILD diagnosis date
- Continuous enrollment with medical and pharmacy coverage for 12 months prior to the fibrosing ILD diagnosis date (***pre-ILD baseline period***)

Exclusion Criteria

- Fibrosing ILD diagnosis in the 12-month pre-ILD baseline period
- Unknown gender or geographic region

Cohort Assignment

Patients meeting initial selection criteria for Aim 1 will be assigned to cohorts based on known cause of fibrosis:

- **IPF**— ≥ 2 medical claims with diagnosis for IPF in any position during the study period
- **Non-IPF ILD**— < 2 medical claims with diagnosis for IPF during the study period

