7.2.3 Study population: Aim 2 [REDACTED]

The analysis for Aim 2 and Further Aim will include patients identified for Aim 1 in Section 7.2.2 who meet the following additional selection criteria. Final oxygen therapy cohorts will be determined during the propensity score matching (PSM) procedure outlined in Section 7.6.2.2.

- **Oxygen therapy cohort**

- ILD patients with ≥ 1 medical claim for oxygen therapy after fibrosing ILD diagnosis. The ***index date*** will be defined as the first date of a claim for oxygen therapy.

- **No oxygen therapy cohort**
 - Matched to a patient in the oxygen therapy cohort. The **index date** will be assigned as a date that is eligible to set an index date (i.e., similar to the matched oxygen therapy patient in time from the fibrosing ILD diagnosis date to the index date, and during the same continuous enrollment period as the fibrosing ILD diagnosis date).

NOTE: Following review of results from Aim 1, the study team will determine whether criteria for Aim 2 and Further Aim require revision.

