7.3.1 Aim 1 Outcomes

7.3.1.1 Primary Outcomes

- **Oxygen Therapy**—Evidence of oxygen use will be captured in the pre-ILD baseline and Aim 1 follow-up periods based on the presence of ≥ 1 diagnosis (ICD-10-CM), procedure (HCPCS, CPT), or revenue code for oxygen therapy. Among patients with oxygen therapy in follow-up, the following aspects of oxygen therapy will be described:
 - **Time to oxygen therapy initiation**—The time in days from the fibrosing ILD diagnosis date to oxygen therapy initiation, among patients without evidence of oxygen therapy in the pre-ILD baseline period.
 - **Sustained oxygen therapy use**—Using claims, sustained oxygen therapy use will be defined among patients with at least 12 months of follow-up after the index date (oxygen initiation date), as a binary variable for the presence of ≥ 11 claims for oxygen therapy in a 12-month period. The following aspects of sustained oxygen therapy will be described:
 - **Time to sustained oxygen therapy use**—The time in days between the index date and the earliest date that defined the sustained oxygen therapy use.
 - **Sustained oxygen therapy use within the first 12 months of follow-up**—The number of patients with the evidence of sustained oxygen therapy use during the first 12 months of follow-up.
 - **Note:** As a sensitivity analysis, sustained oxygen therapy use will also be defined as ≥ 6 claims for oxygen therapy in a 12-month period and, based on the distribution of the count of claims among the population, as the 75th percentile of claims in a 12-month period.

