7.3.5.3 Healthcare Utilization Characteristics

- **Provider specialty**—A count of unique days with a non-inpatient claim for treatment by provider specialty category (primary care physician [including general/family practice, internal medicine], pulmonology and rheumatology) will be reported.
- **Medication use**—ILD medication use will be captured at the class level, including administrations and prescription fills. The number of prescriptions fills within each class will also be calculated. Treatment categories will include corticosteroids (methylprednisone, prednisone, prednisolone), biologics, (abatacept, denosumab, etanercept, tocilizumab, infliximab, rituximab), calcineurin inhibitors (cyclosporine, tacrolimus), and other immunosuppressants (mycophenolate mofetil, hydroxychloroquine, leflunomide, methotrexate, sulfasalazine, chloroquine phosphate).
- **All-cause HCRU**—HCRU will be calculated for ambulatory visits (physician office and hospital outpatient), emergency department (ER) visits, inpatient admissions, and pharmacy fills.
- **All-cause health care costs**—Health care costs will be presented as standardized costs. Total costs will be calculated and presented in categories of pharmacy costs and medical costs (outpatient, inpatient, professional services). Costs will be adjusted using the annual medical care component of the Consumer Price Index (CPI) to reflect inflation between the date of the claim and the most recent year for which the annual CPI is available.

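### The visible Aim 2 criteria and covariates do not identify hospice or end-of-life care, so oxygen started because death is expected can bias the mortality comparison toward apparent harm

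*Combined protocol and SAP*

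**What the plan says.** **Entry and time zero.** In the abstract, the oxygen cohort needs at least one "medical claim for oxygen therapy after fibrosing ILD diagnosis. The index date will be defined as the first date of a claim for oxygen therapy". Section 7.2.3 likewise requires at least one "medical claim for oxygen therapy after fibrosing ILD diagnosis", and the first such claim is the index date. Section 7.3.1.1 captures oxygen use "based on the presence of ≥ 1 diagnosis (ICD-10-CM), procedure (HCPCS, CPT), or revenue code for oxygen therapy". Nothing visible limits the setting, purpose or duration of the oxygen. The sustained-use definition (11 or more claims in 12 months) is an Aim 1 outcome and does not restrict the Aim 2 exposure in 7.3.2.

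**Exclusions.** Aim 2 inherits the Aim 1 criteria. Section 7.2.2 excludes "Fibrosing ILD diagnosis in the 12-month pre-ILD baseline period" and unknown gender or region; the abstract adds unknown insurance type.

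**Covariates.** The Aim 2 list in the abstract gives "clinical characteristics (underlying ILD type; respiratory diseases; other clinical characteristics; Quan-Charlson comorbidity score; AHRQ comorbid conditions; smoking; pulmonary rehabilitation", together with demographics, provider specialty, medication use, utilisation and cost. Section 7.3.5.3 states that "HCRU will be calculated for ambulatory visits (physician office and hospital outpatient), emergency department (ER) visits, inpatient admissions, and pharmacy fills"; hospice is not a category.

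**Outcome and purpose.** The abstract's primary Aim 2 outcomes are "Time to disease progression; time to all-cause mortality; time to hypoxemia, time to acute exacerbations, counts of acute exacerbations". Under 7.3 follow-up begins on the index date, with no visible lag or minimum. Section 5 says the study will judge whether oxygen makes outcomes better or worse, which is a causal question.

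**The concern.** The abstract says that oxygen "is commonly prescribed in clinical practice for patients with fibrotic ILD to reduce breathlessness and increase physical capacity". It is a modest inference, though not a statement in the documents, that some oxygen given for breathlessness is comfort care for patients already expected to die. In those patients the approaching death prompts the exposure.

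Such a patient enters the oxygen cohort on the date of the earliest oxygen claim and may die soon afterwards. Matching cannot balance a state that is not recorded, so the matched control may have a similar claims history without being near death. Early deaths would then collect disproportionately in the oxygen cohort. The result could be an apparent harm or a masked benefit. The feasibility count of 34,299 in 7.5 rests on different criteria, but it suggests a cohort large enough for such a bias to appear with a narrow confidence interval.

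**Working it through.** The plan states no mortality rate, effect size or power calculation, so there is no figure to reproduce. The check has two parts.

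**1. What the visible text records.**
- Eligibility (abstract, 7.2.2, 7.2.3): no hospice, palliative or end-of-life criterion in either cohort.
- Covariates (abstract, Table 1, 7.3.5): no such variable. Section 5 names opioids among common treatments, but the medication classes in 7.3.5.3 omit them, so that partial marker is missing too.
- Proxies that are listed: acute respiratory failure, lung cancer and heart failure (7.3.5.2); inpatient admissions and costs (7.3.5.3).
- Possible further information: Table 1 places hypoxemia in the pre-index baseline, and 7.3.3.1 captures pre-index lung function in the EHR subset. The visible text does not say whether either enters the propensity score.
- Timing: 7.3 defines a 12-month pre-index baseline, but 7.8 describes matched patients as alike on pre-ILD characteristics. The latter period can end long before oxygen starts.

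**2. How large the effect could be.** All inputs here are assumptions. Let p be the share of initiators at the end of life, mh their 90-day mortality, and m0 the 90-day mortality of everyone else, including all controls. Oxygen has no effect and matching removes nothing.

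Risk in the oxygen cohort = p × mh + (1 − p) × m0

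Risk ratio = risk / m0 = 1 + p(mh − m0)/m0

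Example: 0.05 × 0.80 + 0.95 × 0.10 = 0.135, and 0.135/0.10 = 1.35.

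| p | m0 | Risk, mh = 60% | RR | Risk, mh = 80% | RR |
|---|---|---|---|---|---|
| 3% | 10% | 0.115 | 1.15 | 0.121 | 1.21 |
| 5% | 10% | 0.125 | 1.25 | 0.135 | 1.35 |
| 10% | 10% | 0.150 | 1.50 | 0.170 | 1.70 |
| 3% | 5% | 0.0665 | 1.33 | 0.0725 | 1.45 |
| 5% | 5% | 0.0775 | 1.55 | 0.0875 | 1.75 |
| 10% | 5% | 0.105 | 2.10 | 0.125 | 2.50 |

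If a share q of controls is also near death, the ratio becomes [m0 + p(mh − m0)] / [m0 + q(mh − m0)]. With p = 5%, q = 2%, m0 = 10% and mh = 80%, it is 0.135/0.114 = 1.18 instead of 1.35. With q = p it is 1.

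A simulation on the time-to-event scale used 60,000 patients per group, a true hazard ratio of 1, a median survival of one month for end-of-life starters and an unadjusted Cox model:

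| Annual mortality of others | Share | HR, 12 months | HR, 24 months |
|---|---|---|---|
| 10% | 2% | 1.20 | 1.10 |
| 10% | 5% | 1.48 | 1.24 |
| 10% | 10% | 2.03 | 1.56 |
| 20% | 2% | 1.09 | 1.05 |
| 20% | 5% | 1.27 | 1.15 |
| 20% | 10% | 1.52 | 1.28 |

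The bias shrinks with longer follow-up. Removing all end-of-life starters returned 12-month hazard ratios of 0.97 to 1.02, which is 1 within simulation error. That assumes perfect identification.

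**The case against.** The strongest objection is that the deciding text cannot be read. Section 7.2.3 leaves the final cohorts to the matching procedure in 7.6.2.2, and no part of 7.6.2 is in the public document. A hospice variable or sensitivity analysis could be there, so a reader must not infer that the plan ignores the problem altogether. What stands is that 7.2.3 and the covariate lists are readable, are the natural place for such a rule, and contain none.

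The premise is also partly external. The documents do not mention comfort-care oxygen or say how common it is, and they also give physical capacity as a reason for prescribing. This limits any claim about size, but not the observation that the criteria admit such patients.

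A reader might infer that the extra deaths fall in the oxygen cohort alone. The documents do not support that: the control pool has no hospice exclusion either, so patients near death can be controls. Nor is the match blind to severity, given the proxies listed above. These points make the bias smaller, but they do not identify patients whose care has turned to comfort.

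Finally, 7.8 concedes residual confounding, and 7.2.3 allows the Aim 2 criteria to be revised after Aim 1 (the abstract limits this to the enrollment criteria). Both statements are general, and neither names an end-of-life rule.

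**Conclusion.** The concern holds as a gap in the visible eligibility criteria and covariates. One oxygen claim sets time zero, mortality is counted from that day, and nothing visible identifies patients already at the end of life. The expected direction is toward apparent harm, provided that such patients are more common among initiators than among their matched controls.

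The size is unknown. The 90-day risk ratios of 1.15 to 2.5 rest on an assumed 3-10% share, 60-80% mortality in that group, 5-10% in all others, no control near death and no correction by matching. They are an upper-end illustration and should not be read as the bias to expect in this study. It would also go too far to conclude that a finding of higher mortality with oxygen would be an artefact; the documents support only that this explanation could not be excluded on the visible plan.

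**What to change.** Add to 7.2.3 and the abstract, for both cohorts: exclude patients with a hospice or end-of-life care claim at any time from fibrosing ILD diagnosis up to and including the index date. For candidate controls, apply the rule on the assigned index date. Report the number excluded in each cohort. If 7.6.2 already deals with this, one sentence in 7.2.3 saying so is enough.

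The cost is one code list and one eligibility line. A small number of initiators is lost, and the conclusions no longer cover comfort-care oxygen. The rule catches only patients with a recorded claim by index, so some bias may remain.

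Starting the mortality analysis at day 31 is not an adequate substitute. With a constant hazard and 60-80% 90-day mortality, 0.4^(31/90) = 73% to 0.2^(31/90) = 57% of end-of-life starters would still be alive and in the analysis. Section 7.3.3.1 also dates every death to the 15th of its month, so survival to day 31 cannot be established exactly.
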